2.3 RISK/BENEFIT ASSESSMENT

2.3.1 KNOWN POTENTIAL RISKS

Overall, this research study poses no more than minimal risks to participants. There are no physical, financial, legal, social, or cultural, risks to the study participants by joining this study. There are slight psychological risks, as described below. There is a slight risk that subjects may experience adverse

psychological reactions such as anxiety or stress as a result of discussing issues related to cancer or barriers to cancer care. We believe that this risk is minimal. We are using survey items that are commonly used in clinical settings and subjects are likely to have had prior exposure to similar types of questions as part of their medical care. Furthermore, in our past studies with white and AA men and women with HNSCC, the overwhelming majority of respondents have said they found the questions that we have asked related to care have not been upsetting.

There is also a slight risk that confidential information about the participant may be accidentally disclosed as study participants may be asked to provide information considered confidential or private during study interviews. The likelihood of this risk is low as all the investigators have been involved in similar research in the past and have not experienced this problem before due to adequate safeguards.

The decision to participate in this research will be voluntary and individuals may refuse to take part or choose to stop taking part at any time. Participants will also be encouraged to take their time when answering questions and may decline to answer any question at any time. If patients become upset talking about their cancer and the barriers that they faced, they will be offered a referral to the Hollings Cancer Center (HCC) Behavioral Medicine program (which is covered by most health insurance programs) or the HCC Social Worker who will offer links to other HCC and community resources.

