As a result of the aforementioned three strategies, retention of subjects is expected to be highly feasible. The scheduled timepoints of navigator-participant interaction (initial surgical consultation, prior to hospital discharge, first clinic visit after hospital discharge) were chosen because these are situations in which the likelihood of contact is ~100%. Although challenges with retention for cancer studies due to mortality (overall and disease-specific) and treatment toxicity are potentially problematic, we do not think that they will limit retention in this feasibility study of NDURE. The rate of on-treatment mortality (during surgery or adjuvant therapy) is quite low (<5%) and the study follow-up does not extend past the completion of therapy. Thus, lack of retention due to mortality is not expected to be significant. Treatment toxicity is potentially a problem, as patients may not want to answer surveys while undergoing treatment or choose to withdraw due to competing treatment demands. We do not expect this to be a problem, however, because NDURE will be integrated into routine clinical care and thus should not create an excess time burden for patients. In fact, it is likely that participation in the intervention, which is expected to improve care coordination and decrease barriers to care, will make this potential source of dropout less likely than other intervention trials. Using NDURE to address individualized barriers to timely HNSCC treatment is a significant strength and innovation of the study and will likely also improve retention relative to historical rates.

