8.5 ADVERSE EVENTS AND SERIOUS ADVERSE EVENTS

8.5.1 DEFINITION OF ADVERSE EVENTS

This trial is considered to carry a low risk to subjects (i.e. has a "no more than minimal risk" designation). As such, this protocol defines an adverse event (AE) as any undesirable sign, symptom, medical, psychological, social, or emotional reaction that is definitely, probably, or possibly related to the study intervention (as described in 8.5.3). Post-surgical treatment toxicity (wound complications, hospital readmissions, etc) is expected for the NDURE and UC care groups and known to be associated with the primary endpoint (PORT delay).⁶⁰ Although it is not hypothesized that the NDURE intervention will decrease the risk of treatment toxicity, it is hypothesized that NDURE will improve patient-provider communication and care coordination about treatment toxicity, thereby decreasing the risk of PORT delay. As a result, data about expected post-surgical treatment toxicity (wound-healing complications, need for additional surgery, unplanned visits to the emergency room, and unplanned hospital readmissions) are assessed in the PBQ-P and PBQ-N (Section 8.4.5) to allow for specific comparison of these types of events between the NDURE and UC arms and their relationship with the primary endpoint (PORT delay).

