8.5.2 DEFINITION OF SERIOUS ADVERSE EVENTS

A serious adverse event (SAE) will be considered any undesirable sign, symptom, or medical condition which is fatal, is life-threatening, requires or prolongs inpatient hospitalization, results in persistent or significant disability/incapacity, constitutes a congenital anomaly or birth defect, is medically significant

and which the investigator regards as serious based on appropriate medical judgment. An important medical event is any AE that may not result in death, be life-threatening, or require hospitalization but may be considered an SAE when, based upon appropriate medical judgment, it may jeopardize the patient and may require medical or surgical intervention to prevent one of the outcomes listed in the definitions of SAEs. As with the definition of AEs provided in 8.5.1, this protocol defines a SAE as an SAE that is definitely, probably, or possibly related to the study intervention (see 8.5.3).

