8.5.3.2 RELATIONSHIP TO STUDY INTERVENTION

All AEs will have their relationship to study procedures, including the intervention, assessed by the PI based on temporal relationship and his clinical judgment. The degree of certainty about causality will be graded using the categories below.

- **Definitely Related** – There is clear evidence to suggest a causal relationship, and other possible contributing factors can be ruled out. The clinical event, including an abnormal laboratory test result, occurs in a plausible time relationship to study procedures administration and cannot be explained by concurrent disease or other drugs or chemicals. The response to withdrawal of the study procedures should be clinically plausible. The event must be pharmacologically or phenomenologically definitive.
- **Probably Related** – There is evidence to suggest a causal relationship, and the influence of other factors is unlikely. The clinical event, including an abnormal laboratory test result, occurs within a reasonable time after administration of the study procedures, is unlikely to be attributed to concurrent disease or other drugs or chemicals, and follows a clinically reasonable response on withdrawal.
- **Possibly Related** – There is some evidence to suggest a causal relationship (e.g., the event occurred within a reasonable time after administration of study procedures). However, other factors may have contributed to the event (e.g., the participant's clinical condition, other concomitant events). Although an AE may rate only as "possibly related" soon after discovery, it can be flagged as requiring more information and later be upgraded to "probably related" or "definitely related", as appropriate.

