9.3 POPULATIONS FOR ANALYSES

The safety analysis set (SAS) is composed of all patients enrolled who receive any part of either the NDURE or UC intervention. The SAS will be used to conduct all safety analyses. Patients will be analyzed based on the intervention received regardless of the assignment at randomization.

The PORT delay analysis set is composed of all patients enrolled in the trial who are:

1. Randomized to NDURE or UC
2. Receive curative intent surgery at MUSC
3. Have an indication for PORT per NCCN Guidelines based on the presence of at least one of the following adverse features on final pathologic evaluation: ENE, positive margin, pT3 or pT4 primary, at least pN1 nodal disease (per AJCC 8th edition for p16-ve non-oropharyngeal SCC or AJCC 7th edition for p16+ve oropharyngeal SCC), nodal disease in levels IV or V, PNI or LVI
4. Are alive for ≥ 6 weeks postoperatively.

Analysis will be performed based on assignment at randomization regardless of the intervention received (modified intent to treat). This analysis set will be used for analysis of the primary endpoint. The rationale for this definition of the PORT delay evaluable set is that eligibility, randomization, and delivery of a portion of the intervention occur prior to definitive treatment of the HNSCC. However, the primary endpoint is evaluable only for patients who undergo surgery for HNSCC, have an indication for adjuvant PORT (which can only be definitively known following surgical resection), and are alive for at least 6 weeks postoperatively. Therefore, we expect that a subset of patients who meet all eligibility criteria will be enrolled in the study, randomized to NDURE or UC, receive a portion of the intervention, but subsequently be non-evaluable for the primary endpoint when information becomes available later in the clinical course that cannot be known at the time of study enrollment and randomization (e.g., they (1) elect a non-surgical treatment option; (2) have no indication for PORT per NCCN Guidelines on final pathologic assessment; (3) have a mortality prior to 6 weeks postoperatively).

The Time-to-PORT (TTP) analysis set is composed of all patients enrolled in the trial who are:

1. Randomized to NDURE or UC
2. Receive curative intent surgery at MUSC

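### Adverse event status is tied to the study intervention in 8.5.1 and 8.5.2 but to all study procedures in 8.5.3.2, and no by-arm safety table or count of all deaths is planned

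*Combined protocol and SAP*

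**What the plan says.** **Definitions.** Section 8.5.1 defines an adverse event as "any undesirable sign, symptom, medical, psychological, social, or emotional reaction that is definitely, probably, or possibly related to the study intervention"; the sentence closes with a reference to 8.5.3. Section 8.5.2 follows suit: "this protocol defines a SAE as an SAE that is definitely, probably, or possibly related to the study intervention", also with a reference to 8.5.3.

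**Relatedness.** Section 8.5.3.2 has a wider object: "All AEs will have their relationship to study procedures, including the intervention, assessed by the PI". Its grades are definite, probable and possible; it has no grade for unrelated. Section 8.5.3.4 collects only events that meet the definition. Section 8.5.3.3 starts recording at consent.

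**Named risk.** Section 2.3.1 expects slight psychological risk from discussing cancer and barriers to care, and offers as reassurance: "We are using survey items that are commonly used in clinical settings". Section 2.3.3 calls such distress a psychological adverse event, without restriction by arm, and provides a referral route.

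**Analysis.** Section 9.3 forms a safety set from patients who receive any part of either NDURE or usual care, analysed by intervention received: "The SAS will be used to conduct all safety analyses". Section 9.4 contains no safety analysis.

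**Deaths.** Under 8.4.4, a patient who dies before PORT and within 6 weeks of surgery is not evaluable for the primary endpoint, and one who dies before PORT but after 6 weeks counts as delayed. Section 9.3 requires survival to 6 weeks for the primary set. Deaths before PORT are censored in the time-to-PORT analysis, with a competing-risk sensitivity analysis. Section 9.4.4.2 does likewise for deaths during PORT in treatment package time.

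**The concern.** Study staff cannot apply two different capture rules to one event. The risk that the protocol itself names, distress from study conversations and surveys, is where the rules diverge. Table 1 gives the questionnaires to both arms, and several are completed at screening, before allocation. Distress at that visit falls inside the recording window but, on the literal wording of 8.5.1, cannot be related to an intervention that has not begun.

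The definition also makes existence as an event depend on attribution. In a non-blinded trial, one person decides whether an event is related, and an event judged unrelated leaves no adverse event record. That person also directs safety oversight (10.1.6). Counts by arm would then mix event rates with willingness to attribute, and attribution to routine care is plausibly rarer than attribution to a new navigation programme.

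Deaths matter for a second reason. Randomization and part of the intervention precede surgery, so removing deaths before 6 weeks is a post-randomization exclusion from the primary set. A reader of the primary result needs to see whether those exclusions are balanced, and no planned table shows it.

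**Working it through.** The plan states no figure on this point, so the check is mainly a comparison of sections, followed by a calculation of scale.

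**1. One event under each rule.** Take a usual care patient distressed by a study questionnaire.
- 8.5.1 and 8.5.2, read literally: not related to the study intervention, so not an event.
- 8.5.3.2: a questionnaire is a study procedure, so the event can be graded as related.
- 2.3.3: a psychological adverse event if it arises from talking about cancer or barriers.
- 8.6.1 (unanticipated problems): relation to research participation is enough, again wider than the intervention.

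The cross-reference to 8.5.3 may import the wider test, but the text does not say so. It is also circular: 8.5.3.2 grades events that 8.5.1 has already admitted as related.

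**2. Where deaths and admissions appear.**
- Primary set: excludes deaths before 6 weeks; later deaths before PORT count as delay.
- Time-to-PORT set: has no survival condition, so early deaths stay in, but only among patients operated on at the study site with a PORT indication.
- Treatment package time set: further restricted to patients who started PORT.
- Full analysis set: used for secondary analyses of the endpoints; no count of deaths is described.
- Readmissions and other surgical toxicity: collected through the PBQ in both arms, without a relatedness filter, for comparison between arms (8.5.1). Section 9.4.9 describes barrier resolution and its association with delay, not these items by arm. Exploratory analyses are complete-case (9.4.2). Death is not among the listed items. The PBQ-N is rated by the navigator (8.4.5), while the usual care nurse navigator stops after the initial consultation (6.1.1.2), and no rater for usual care is named.

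**3. Scale of a deaths table.** Inputs: on-treatment mortality below 5% (5.5); enrolment of 170, maximum 180 (9.2.2); 1:1 allocation (6.3).
- Ceiling, all enrolled: 0.05 × 170 = 8.5; 0.05 × 180 = 9.0.
- Ceiling per arm: 0.05 × 85 = 4.25; 0.05 × 90 = 4.5.
- With 85 per arm and assumed mortality q, expected deaths are 85q and the chance of at least one is 1 − (1 − q)^85:

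| Assumed q | Expected per arm | Chance of at least one |
|---|---|---|
| 1% | 0.85 | 57% |
| 3% | 2.55 | 92% |
| 5% | 4.25 | 99% |

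**4. Why descriptive only.** Power of the two-sided pooled Z-test is Φ{[d − 1.645·√(2p̄(1−p̄)/n)] / √([p₁(1−p₁)+p₂(1−p₂)]/n)}, where d is the difference between p₁ and p₂ and p̄ is their mean. For the plan's own primary comparison (45% against 25%, n = 75 per arm, α = 0.10) it gives (0.2 − 0.1281)/0.0762 = 0.944, or 82.7%, against the stated 83%. For deaths of 5% against 10% with n = 85 it gives (0.05 − 0.0665)/0.0402 = −0.409, or 34%. A test would say little, but counts would still be informative.

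**The case against.** The strongest defence is that this is a minimal-risk navigation trial with a deliberate, stated design. Section 8.5.1 explains that surgical toxicity is expected in both arms and captured separately, and limiting events to related ones avoids a flood of surgical complications. That reasoning stands, and it supports keeping expedited reporting narrow. It does not explain why the definitions and the grading scale differ, or why the safety set has no analysis.

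Several stronger readings are tempting, and the documents do not support them:
- *Survey distress is plainly left out.* The cross-reference to 8.5.3 and the wording of 2.3.3 point the other way. The finding is a contradiction to reconcile.
- *Usual care has almost no events by construction.* Section 9.3 and Table 1 treat usual care as an intervention, so events related to it can qualify. Under-attribution is plausible but remains an inference.
- *Admissions count only if judged related.* The PBQ records unplanned readmissions in both arms without that filter.
- *Early deaths appear in no planned analysis.* Those in operated patients with a PORT indication are in the time-to-PORT set and its competing-risk sensitivity analysis by arm.
- *Stopping decisions see only attributed events.* The monthly review in 10.1.6 also covers unanticipated problems, early withdrawals and endpoint data, and the grounds in 10.1.2 are not exhaustive.

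One practical objection also stands. Section 7.2 allows the investigator to discontinue patients who choose non-surgical or outside treatment or who have no PORT indication, so complete death follow-up in everyone randomized is not assured.

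**Conclusion.** The point holds as an inconsistency plus a gap in reporting. The definitions in 8.5.1 and 8.5.2 conflict with 8.5.3.2 and 2.3.3; the literal reading drops events that the protocol elsewhere calls adverse events; and counts by arm depend partly on unblinded attribution. A safety set is defined without an analysis, and all deaths are not counted by randomized arm.

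The size is modest. Applying the 5% ceiling to everyone enrolled gives at most about 8.5 to 9 deaths, roughly 4 per arm. This bound is generous, because some enrolled patients never have surgery or PORT. The 1% to 5% range is an assumption, since the documents give only an upper limit, and the per-arm probabilities treat deaths as independent. The number falling before 6 weeks cannot be derived from the documents. Neither the sample size nor the planned power changes.

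**What to change.** 1. In 8.5.1 and 8.5.2, replace the condition of relatedness to the intervention with the scope already used in 8.5.3.2 (study procedures, with the intervention among them), and state that this covers study questionnaires in both arms.
2. In 9.4, add one descriptive table by randomized arm, in all randomized patients, of adverse events and serious adverse events as defined. Regardless of relatedness, add known deaths from any cause (before 6 weeks, later before PORT, during PORT) and the unplanned readmissions already collected through the PBQ. Show patients discontinued or of unknown status on separate lines. Because 9.3 analyses the safety set by intervention received, label the table's population clearly.
3. Leave expedited reporting limited to related events.

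The cost is a few words in two definitions and one table. Dates of death before PORT are already needed for the endpoint rules, and readmissions are already asked about. The downside is a slightly longer event listing, mostly of unrelated events, and an incomplete death count for discontinued patients, which the separate lines make visible.

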1.3 SCHEDULE OF ACTIVITIES

Table 1. Schedule of Activities for NDURE and Usual Care: Screening, Treatment, and Follow-up								
Study Period		Screening	Allocation	Treatment			Follow-Up	
Visit Label	Visit #			Pre -Op	Pre - D/ C	Post - D/C		
Visit Label	Visit #	1	--	2	3 ^{a,b}	4 ^c	5 ^d	6 ^e
Study Activity								
Enrollment	Eligibility Screen	X						
	Informed Consent	X						
Allocation	Allocation		X					
Study Intervention	NDURE			X	X	X	X	
	Usual Care			X	X	X	X	
Study Assessments								
Baseline	Demographics	X						
	Baseline Oncologic Characteristics	X						
	Charlson-Deyo Comorbidity Index	X						
	PORT Delay Nomogram	X						
	Lukwago Cultural Questionnaire	X						
Safety	Adverse Events			←		→		
Efficacy	Surgical Details				X			
	PORT Start Date						X	
Fidelity	NDURE Fidelity						X	
Feasibility	NDURE Accrual	X						
	NDURE Completion			X	X	X	X	
	Navigator Caseload			←		→		
	Navigator Time Allocation			X	X	X	X	
Acceptability	PSN-I Questionnaire						X	
	Semi-Structured Interview						X	
	Program Evaluation Questionnaire						X	
Barriers to Timely PORT	PBQ-Patient Questionnaire			X	X	X	X	
	PBQ-Navigator			X	X	X	X	
	Presurgical RT Consult						X	
	Pre-RT Dental Extractions						X	

Table 1. Schedule of Activities for NDURE and Usual Care: Screening, Treatment, and Follow-up								
Study Period		Screening	Allocation	Treatment			Follow-Up	
Visit Label	Visit #			Pre-Op	Pre-D/C	Post-D/C		
		1	—	2	3 ^{a,b}	4 ^c	5 ^d	6 ^e
Study Activity								
Cancer Care Delivery Processes	Date Pathology Report Returned						X	
	Date of Postoperative Referral to Radiation Oncology						X	
	Date of Postop Appointment with Radiation Oncology						X	
	Date of CT Simulation						X	
Adjuvant Therapy Details	Type of Adjuvant Therapy						X	
	PORT Completion Date						X	
	Radiation and Medical Oncology Facility						X	
Health Behavior Constructs	CTM-15 Questionnaire				X	X		
	ISEL-12 Questionnaire	X					X	
	PSQ Questionnaire	X			X	X		
	IPQ-R Consequences Questionnaire	X			X	X		
	CASE-Cancer Questionnaire	X					X	

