
^a Study Visit 5 assessments are to be administered after the start of PORT. For the purposes of determining when to administer Study Visit 5 assessments, the study coordinator will determine that a patient has started PORT either by verifying in the EMR (for patients undergoing PORT at MUSC) or by contacting the patient no sooner than 8 weeks after surgery (for patients undergoing PORT outside of MUSC). If PORT is indicated but never initiated, Study Visit 5 assessments are to be completed 12 weeks after surgery.
 
^b Following completion of PORT, the study coordinator will gather all of the required source documentation to ascertain efficacy and cancer care delivery endpoints as well as adjuvant therapy details
							

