Function 4: Improve communication between patient and providers regarding intentions and goals for timely, guideline-adherent PORT.

Form: Standardized discussion of expected indication for PORT and choice of radiation facility at initial consultation. At the initial surgical consultation, the clinician informs the patient that based on his/her clinical stage, it is expected that treatment will include a package of surgery and PORT. At this same clinical encounter, the NDURE navigator facilitates a discussion with the patient and clinician to help the patient decide at which facility he/she will receive PORT.

Function 5: Enhance coordination of care between healthcare teams during care transitions and about treatment sequelae.

Form: NDURE PORT Care Plan. At each navigation encounter, the NDURE navigator meets with the patient, caregiver, and clinicians to generate (and update) a PORT Care Plan. The NDURE PORT Care Plan is an EMR-based document that (a) captures clinical factors and the care delivery processes necessary to start PORT; (b) describes the patient's barriers to timely PORT; and (c) documents the patient's personalized Barrier Reduction Plan.

Function 6: Restructure the organization to clarify roles and responsibilities for care processes associated with PORT delivery to avoid duplication and gaps in care.

Form: NDURE Navigator makes referrals and schedules appointments to optimize adherence with key PORT care delivery process. The NDURE navigator is assigned sole responsibility for making all PORT-related referrals (and scheduling appointments) with radiation and medical oncology, dentistry, and oral surgery in a manner that optimizes adherence to the following care delivery processes associated with timely PORT.

- (1) Prior to surgical resection, the patient has consultation with a radiation oncologist at the facility where the patient intends to receive PORT.
- (2) Prior to surgical resection, the patient has a consultation with a dentist and oral surgeon (if indicated) and subsequently undergoes extraction of indicated teeth at the time of surgical resection.
- (3) Engaging with the pathologist if the pathology report is not issued by postoperative day 8. Upon receipt of the pathology report, promptly communicating key pathologic findings to the HN team to facilitate formation of a plan for pathology-directed adjuvant therapy.

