8.4.5 BARRIER TO TIMELY PORT ASSESSMENTS

Perceived Barrier Questionnaire-Patient (PBQ-P): The PBQ-P is a 17-item self-report measure of barriers to timely initiation of PORT, as assessed by the patient. Each item is scored as yes/no. Versions of this questionnaire have been used extensively to assess perceived barriers in prior PN studies^{11,44,51,52}. Each item is scored as yes/no. The total score is calculated by summing the individual responses. PBQ-N scores range from 0-17; higher scores reflect greater barriers to timely PORT.

Perceived Barriers Questionnaire-Navigator (PBQ-N): PBQ-N is a 17-item measure of barriers to timely initiation of PORT, as assessed by the PN. Each item is scored as yes/no. Versions of this questionnaire have been used extensively to assess perceived barriers in prior PN studies^{11,44,51,52}. Each item is scored as yes/no. The total score is calculated by summing the individual responses. PBQ-P scores range from 0-17; higher scores reflect greater barriers to timely PORT.

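### The between-arm toxicity comparison closes at PORT start for patients irradiated at MUSC, so NDURE's look-back is on average shorter; the artefact is probably small and cheap to remove

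*Combined protocol and SAP*

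**What the plan says.** Section 8.5.1 limits adverse events to those at least possibly related to the intervention. Expected surgical toxicity (the four event types above) is instead assessed on the PBQ-P and PBQ-N, with the stated purpose "to allow for specific comparison of these types of events between the NDURE and UC arms", and also to relate these events to PORT delay. The same section says that NDURE is not expected to reduce toxicity.

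Section 8.4.5 describes the PBQ: "Each item is scored as yes/no". It gives no recall period and no event date. Table 1 in Section 1.3 schedules the "PBQ-Patient Questionnaire" and its navigator counterpart at Visits 2 to 5 and marks neither at Visit 6.

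The Table 1 footnote on Visit 5 sets no postoperative day: "Study Visit 5 assessments are to be administered after the start of PORT". The coordinator establishes PORT start in one of two ways:
- At MUSC: "by verifying in the EMR (for patients undergoing PORT at MUSC"), with no minimum interval.
- Elsewhere: "by contacting the patient no sooner than 8 weeks after surgery (for patients undergoing PORT outside of MUSC").

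For non-starters: "If PORT is indicated but never initiated, Study Visit 5 assessments are to be completed 12 weeks after surgery".

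Section 9.1.2 hypothesises a shorter median time-to-PORT with NDURE. Under Function 4 of Section 6.1.1.1, "the NDURE navigator facilitates a discussion with the patient and clinician to help the patient decide at which facility he/she will receive PORT". Section 9.4.9 plans analyses of unresolved barriers but no toxicity comparison at a fixed day or adjusted for time.

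**The concern.** A yes/no item asked repeatedly until a closing visit records whether an event has happened by that visit. If the closing visit comes earlier in one arm, that arm has less time in which to answer yes, even when the true event rates are equal. At MUSC the closing visit follows PORT start, which NDURE aims to move. Where PORT is given decides which Visit 5 rule applies, and the navigator takes part in that choice too.

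The plan has no other route to this comparison. Adverse-event recording runs to the end of follow-up (Section 8.5.3.3) but excludes unrelated surgical toxicity, and the non-baseline data in Section 8.3 include no dates for these events. At stake is the one stated between-arm comparison of post-surgical complications and readmissions, which could lean towards NDURE when nothing differs.

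**Working it through.** **Inputs from the plan.** PORT delay beyond day 42 is 45% in usual care and 25% in NDURE, with 75 patients per arm (Section 9.2.2). The Visit 5 rules are those of Table 1. As a proxy for PORT outside MUSC I use the 51% of cases that cross healthcare systems (Section 2.2.5), a background figure and not this trial's mix.

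**The plan's own figure.** With pooled proportion 0.35, the null SE is √(2×0.35×0.65/75) = 0.0779. The alternative SE is √((0.45×0.55 + 0.25×0.75)/75) = 0.0762. Power = Φ((0.20 − 1.645×0.0779)/0.0762) = Φ(0.94) = 82.7%, against the stated 83%.

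**Assumptions, not in the documents.** Every patient starts PORT. Visit 5 falls on the PORT start day (MUSC) or on the later of day 56 and PORT start (elsewhere). True toxicity is identical in both arms, 20 to 40% by day 42, at either a constant hazard or one decaying with a 14-day constant. Event times are independent of PORT start. Time-to-PORT follows one of two shapes, each matched to 45% and 25% beyond day 42.

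**Window at MUSC, lognormal.** Mean = 42·exp(−zσ + σ²/2), with σ = √ln(1+CV²) and z = 0.126 (usual care) or 0.674 (NDURE).
- CV 0.20, σ = 0.198: 41.8 versus 37.5 days, gap 4.3.
- CV 0.35, σ = 0.340: 42.6 versus 35.4 days, gap about 7.3.

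**Window at MUSC, normal, values outside 14 to 126 days set to the limit.** At SD 14 the means before limiting are 42 − 0.126×14 = 40.2 and 42 − 0.674×14 = 32.6. After limiting they are 40.4 and 33.2, gap 7.2. At SD 10 and SD 20 the gaps are 5.4 and 9.2. The two shapes together give about 4 to 9 days.

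**Outside MUSC.** The day-56 floor applies in both arms. At SD 14 the means are 56.9 and 56.3 days, gap 0.6.

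**Mixed, 51% outside MUSC.** 0.49×40.4 + 0.51×56.9 = 48.8 days, and 0.49×33.2 + 0.51×56.3 = 45.0 days.

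**From days to percentage points.** With 30% by day 42 and a constant hazard, λ = −ln(0.7)/42 = 0.00849 per day. At the mixed mean windows, 1 − exp(−48.8λ) = 33.9% and 1 − exp(−45.0λ) = 31.8%, about 2.2 points before rounding. Averaging over the whole distribution gives 2.3. The simulated ranges (normal model, SD 10 to 20, toxicity 20 to 40%) are:

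| PORT location | Window gap (days) | Spurious difference, constant hazard (points) | Spurious difference, front-loaded (points) |
|---|---|---|---|
| MUSC only | 5.4–9.2 | 2.4–7.0 | 0.6–2.2 |
| 51% outside MUSC | 2.8–5.3 | 1.2–3.9 | 0.3–1.1 |
| Outside MUSC only | 0.2–1.5 | 0.1–0.8 | at most 0.04 |

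As a share of the events usual care would report at MUSC, the lognormal model at a constant rate loses 1 − 37.5/41.8 = 10% to 1 − 35.4/42.6 = 17%. With exponential event times of mean 14 to 30 days the loss is 2 to 9%.

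**Noise for comparison.** With 75 per arm and 30% toxicity, the SE of the difference is √(2×0.3×0.7/75) = 7.5 points.

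**The case against.** The PBQ measures barriers to starting PORT, and an event after PORT starts cannot be one, so surgery to PORT start is the natural window for that purpose. This stands for relating toxicity to delay. It does not serve the other purpose Section 8.5.1 states, a comparison of event types between arms.

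A reader might infer that NDURE will look safer by construction. The documents do not support that. The direct link to PORT start exists only at MUSC. Visits 3 and 4 are not triggered by PORT start and would record early complications. Who completes the navigator-assessed PBQ-N in usual care is not stated, and closer navigator contact could raise NDURE counts. A shift of patients to MUSC would enlarge the artefact, but no document gives a shift of any size.

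A reader might also infer that the windows cannot be equalised from PBQ data. That is too strong: answers belong to a visit, so the arms can be compared through Visit 4. The form itself is not in the documents, so it may ask for more than Section 8.4.5 describes.

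The 12-week rule for non-starters adds almost nothing in the lognormal model, where about 0.04% of usual-care patients at CV 0.35 have no PORT by day 126. The actual number of non-starters is unknown.

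The model also simplifies. Visit 5 need only follow PORT start, and an equal lag in both arms would shrink the relative gap. Section 8.5.1 says that toxicity is associated with delay, so window length partly results from the outcome itself. That limits the figures, and it favours a fixed window over dividing by time at risk.

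**Conclusion.** The point holds in limited form. As written, PBQ-P ascertainment of post-surgical toxicity closes earlier on average in NDURE for PORT at MUSC, by about 4 to 9 days under the assumed distributions, which tends to under-count NDURE events. Over a mixed population the artefact is about 0.3 to 4 percentage points: the low end if toxicity is early, the high end at a constant hazard with 40% toxicity and wide spread. It is small against a standard error near 7.5 points, so it is unlikely on its own to make a true null read as fewer complications. The net direction for the PBQ-N is uncertain. The mechanism follows from the text. The sizes are illustrative, because event rates, time-to-PORT spread and site mix are not given. The point is minor to moderate: the comparison is descriptive, with no specified test and no safety claim.

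**What to change.** In Section 8.5.1:
- Base the between-arm comparison on one common window from definitive surgery, in both arms as randomized. Day 0 to 42 is an example that matches the primary endpoint's limit.
- Record a date for each of the four event types, from a PBQ-P prompt plus the EMR and outside records.
- Flag events after PORT start. NDURE patients will on average spend more of a day 0–42 window on radiation, so an unflagged count could lean against NDURE.
- As a supporting analysis with no new data, compare PBQ responses cumulatively through Visit 4. Visit 4 has no fixed day either, and it is omitted for patients not discharged before PORT.
- Do not use the cumulative PBQ through Visit 5 as the arm comparison. Report the Visit 5 day by arm.

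The window difference is then zero by definition. The cost is four date fields and some added abstraction: the records gathered at Visit 6 are now specified for efficacy, care-delivery and adjuvant-therapy data, not for these events. Events after day 42 would be listed only descriptively, and emergency visits at outside facilities would rely on patient-reported dates. Neither care nor the primary analysis changes.
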